We have included placebo control conditions for each study drug, to assist with interpretation of the study results. Since this study will recruit healthy individuals and we will not be removing access to a known treatment, we believe that inclusion of the placebo conditions poses low risk to participants.

- f. Definition of treatment failure or participant removal criteria.

Participants will be removed from the study if they remove their consent to participate, become pregnant, refuse to adhere to the study session schedule, or if it becomes clear that their continued participation could put them at increased risk (e.g., develop a chronic pain condition that requires treatment, onset of a medical/psychiatric disorder). These decisions will be made in conjunction with the BPRU medical team.

- g. Description of what happens to participants receiving therapy when study ends or if a participant's participation in the study ends prematurely.

N/A

5. Inclusion/Exclusion Criteria

Inclusion Criteria:

- Aged 18-75
- Urine sample tests negative for common illicit substances of abuse, including cannabis
- Medically cleared to take study medications

- Are not pregnant or breast feeding
- Willing to comply with the study protocol.

Exclusion Criteria:

- Meet DSM-5 criteria for alcohol/substance use disorder
- Taking opioids for pain
- Previous adverse reaction to a cannabinoid product
- Prescribed and taking stimulants or benzodiazepines
- Answer “yes” to item 1 of the Brief Pain Inventory indicating chronic pain
- Self-report any illicit drug use in the past 7 days
- Presence of any clinically significant medical/psychiatric illness judged by the investigators to put subject at elevated risk for experiencing an adverse event
- History of seizure disorder
- Have a known allergy to the study medications or sesame seed oil
- Taking medications contraindicated with hydromorphone or dronabinol
- Have a history of clinically significant cardiac arrhythmias or vasopastic disease
- Have an abnormal and clinically-significant ECG
- Failure to discriminate between hydromorphone and placebo in the Screening 2/Qualifying session.

6. Drugs/ Substances/ Devices

- a. The rationale for choosing the drug and dose or for choosing the device to be used.

Study Drugs: Hydromorphone and dronabinol will be over-encapsulated by our research pharmacy and administered orally.

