Hydromorphone (Dialudid) is a potent mu-opioid agonist that we have extensive experience administering in controlled laboratory settings. Hydromorphone is not subject to differences in CYP metabolic enzymes (in contrast to other opioids such as oxycodone) and therefore will not require us to screen out individuals with recent exposure to CYP inhibitors/inducers, or to analyze/statistically control for CYP metabolic profiles. We have selected a 4mg oral hydromorphone dose for this study because we have data from another ongoing study (IRB00047423) indicating it produces a mild-moderate effect (versus a ceiling or floor effect) and will therefore allow us to visualize changes as a function of the dronabinol. 4mg oral hydromorphone is also a dose that is commercially available and regularly prescribed for analgesia, which increases the clinical relevance of this study. Based on clinical experience, we expect it to produce a moderate analgesic effect on pain. This is an important feature because too strong a dose could overwhelm the cannabinoid effect and prevent us from effectively evaluating the study hypotheses. A moderate dose of hydromorphone will better enable us to evaluate shifts in the analgesic curve as a function of the study drug, and provide a stronger assessment of whether cannabinoids will enhance the analgesic effect of hydromorphone.

Study Drug Dosing		
Condition	Hydromorphone Oral	Dronabinol Oral
Nonrandomized 1	4mg	Placebo
Randomized 2	4mg	2.5mg
3	4mg	5mg
4	4mg	10mg
5	placebo	placebo
Session 1 will be nonrandomized and used as a safety screening day. Sessions 2-5 will be randomized and counter-balanced across participants.		

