- **Primary Aim 1:** The primary outcome will be the area under the curve of each QST procedure, which will provide an assessment of the mean duration and magnitude of the drug effect. Primary outcomes will be tested with repeated two-factor (Drug Condition x Time) models to examine main and interaction effects for all raw data as designed. If there is large variation across subjects at the baseline timepoint, the raw data will be transformed as a change from baseline and analyzed in drug condition by time models. Statistical analyses will be conducted using multilevel analyses with an autoregressive covariance structure using SAS PROC MIXED Software¹³¹. These analyses will permit an examination for effects of drug condition and time effects associated within the course of the study. Interpretation of drug condition main effects and interactions will rely on Tukey post-hoc tests. This aim will also assess frequency of adverse events as a function of study drug.

Specific outcome variables for the QST procedures will be as follows:

- a. Heat Pain Threshold and Tolerance: HPT_h and HPT_o in °C (both in normal and capsaicin treated skin)
 - b. Pressure Pain Threshold: PPT_h in kilopascals
 - c. Thermal and Mechanical Temporal Summation: Verbal pain ratings (both in normal and capsaicin treated skin for MTS)
 - d. Conditioned Pain Modulation: The index score of CPM:PPT_h and CPM:TS (compared to baseline) for each dose
 - e. Cold Water Tolerance: Time to tolerance (compared to baseline) for each dose.
- **Primary Aim 2:** The Drug vs. Money questionnaire will be compared across dose conditions, using peak monetary rating for each dose as the primary outcome. Within-subject changes, as a function of dose, will be analyzed using a repeated measures analysis of variance (ANOVA).
 - **Primary Aim 3:** Neurocognitive tests will be compared as a function of study drug dose, using study session number (1-6) as a covariate to control for practice effects. Specific outcome measures will include:
 - a. Divided Attention Task (DAT): Accuracy with which they perform the two tasks
 - b. Digit Symbol Substitution Task (DSST): Accuracy, total number of patterns completed in allotted time
 - c. Computerized version of the Paced Auditory Serial Addition Task (PASAT): Summed of correct trials

b. Secondary outcome variables.

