Demographic and drug use characteristics, including a positive signal (defined as >20 points rating from baseline on VAS rating of Drug Effect from Session 1), that are hypothesized a priori to be associated with outcomes (e.g., Body Mass Index) will be compared across sex groups and significant differences will be included as covariates in the subsequent analyses. All analyses will be repeated and sex (male/female) will be added as a factor to the analyses.

c. Statistical plan including sample size justification and interim data analysis:

Since this will be the first study to examine the effect of cannabinoids on opioid-induced analgesia using a within-subject laboratory model of pain, there are no data available upon which a power analysis may be directly based. Therefore, we have used G-power to estimate our sample size. We estimate that a within-subject comparison using peak change from baseline as the primary outcome measure and comparing 6 medication conditions will yield power of 0.95 to detect a main effect at even a low effect size (0.2) by enrolling a sample size of 45. For each study, we are proposing to enroll 60 subjects to ensure we will have 50 study completers, and we will enroll equal quantities of men and women to examine sex-based differences in responding. This approach will result in an overall completion sample of 50 per study, with subsamples of 25 per group, which is consistent with other within-subject evaluations of drug effects. This sample size has been powered to support within-subject effects of study drug and between-subject effects of sex on study outcome measures.

d. Early stopping rules.

The safety of participants is a priority of BPRU. The largest potential risk of this study is cardiovascular in nature. This notion is based upon the results of a published study that reported an increase in heart rate and blood pressure

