c. Capsaicin: Capsaicin is the main ingredient in hot peppers, and is used as an over the counter drug for the treatment of pain. The dose of capsaicin we are using is higher than what is available over the counter, although it is less than half of the dose in a single habanera pepper. Capsaicin does cause pain, like a hot pepper may do when it is eaten. Capsaicin may produce some local redness and swelling that will disappear within a day. The area of skin where the capsaicin is applied could be sensitive for up to 48 hours. Capsaicin may cause a burning feeling in the eyes or other areas of the body if accidentally rubbed onto other skin areas.

d. Chance That Participants May Begin Abusing Opioids or Cannabinoids Following Exposure to Study Drugs: There is a small but potential risk that exposing non-drug abusing individuals to doses of hydromorphone or cannabinoids may elicit reinforcing effects that could precipitate subsequent drug-use behavior. Enrolling non-drug users into controlled laboratory studies is a conventional strategy that has been used extensively to evaluate the abuse liability potential of numerous drugs of abuse both within our laboratory and by other laboratories.

e. Discomfort from Pain Testing: Participants will likely find the pain testing procedures uncomfortable for a brief period of time. This effect is expected to be transient and to produce only mild levels of discomfort.

f. Breach of Confidentiality: Although staff members are highly trained to maintain participant confidentiality, there is always a risk that some of the confidential information collected could be revealed to people who are not involved in the research study. This could be embarrassing to the participant if the participant preferred to keep his or her study participation secret, or if sensitive information became known to an individual outside the study. We have an extensive history of conducting research among substance abusers and have instituted several practices to prevent a breach from confidentiality from occurring (see below); thus, we believe this risk to be minimal.

b. Steps taken to minimize the risks.

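### Aim 2 predicts no increase in abuse liability, but nothing requires Drug vs. Money to separate hydromorphone from double placebo before a non-significant result counts as support

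*Combined protocol and SAP*

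**What the plan says.** - **Role of placebo.** Section 4.e: "We have included placebo control conditions for each study drug, to assist with interpretation of the study results". It does not say how they will assist.
- **Conditions.** The dosing table in section 6.a has five: hydromorphone 4 mg with dronabinol placebo, 2.5, 5 or 10 mg, and double placebo. Hydromorphone + placebo is always Session 1. The other four are randomized over Sessions 2 to 5. No condition gives dronabinol alone.
- **Aim 2.** The hypothesis in section 2 is that dronabinol does not increase positive subjective ratings or other abuse-liability proxies relative to hydromorphone alone. Section 7.a: "The Drug vs. Money questionnaire will be compared across dose conditions", using peak monetary rating and a repeated-measures ANOVA. It gives no named contrast, no margin and no rule for reading a null.
- **Aim 1.** Section 7.a uses drug condition by time models with Tukey post-hoc tests for each QST measure. Hydromorphone versus double placebo is among the Tukey pairs, but nothing depends on it. On the dose, section 6.a says "Based on clinical experience, we expect it to produce a moderate analgesic effect on pain".
- **Nearest rules.** Section 5 excludes people who fail to discriminate hydromorphone from placebo in a qualifying session. Section 7.b defines a positive signal as a rise of more than 20 VAS points in Session 1. Both classify participants and neither tests an outcome measure.

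**The concern.** For Aim 2 the hoped-for result is a null. The less sensitive the questionnaire, the more often that null appears, so insensitivity works in favour of the hypothesis. Drug vs. Money asks for hypothetical dollar values from healthy volunteers. The risk section describes the exposure as "exposing non-drug abusing individuals to doses of hydromorphone or cannabinoids". Many might value every dose at or near $0, although the documents give no distribution.

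The double-placebo session is the only one in the trial that can show whether 4 mg hydromorphone moves the questionnaire in these participants. Section 3 says the goal is to find combinations that relieve pain with little abuse liability and to advance them into clinical trials. False reassurance on this outcome would feed into that choice.

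**Working it through.** **1. The plan's own figure.** Section 7.c bases its power on six conditions and claims 0.95 power "to detect a main effect at even a low effect size (0.2) by enrolling a sample size of 45". Alpha, correlation and sphericity are not stated. I assume 0.05, 0.5 and sphericity, and read 0.2 as Cohen's f. The noncentrality is f² × N × m / (1 − ρ).

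- Six conditions, N = 45: 0.04 × 45 × 6 / 0.5 = 21.6 on 5 and 220 df. Power is 0.962, and the smallest sufficient N is 43. The stated figure reproduces approximately.
- Five conditions, as in the dosing table: 0.04 × 45 × 5 / 0.5 = 18.0 on 4 and 176 df. Power is 0.937, and N = 48 is needed for 0.95.

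This power is for an omnibus difference among all conditions. It covers neither hydromorphone versus double placebo nor a claim of no increase.

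**2. Power of the sensitivity check.** Paired t, two-sided 0.05, n = 50 (the completers planned in 7.c), noncentrality dz × √n. The values of dz are assumptions, because the documents give no SDs or expected hydromorphone effect for these outcomes.

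| dz | dz × √50 | Power |
|---|---|---|
| 0.2 | 1.41 | 0.28 |
| 0.3 | 2.12 | 0.55 |
| 0.4 | 2.83 | 0.79 |
| 0.5 | 3.54 | 0.93 |

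With 60 completers (the target in section 4.a), power is 0.63 at 0.3 and 0.97 at 0.5.

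**3. How often a null would count.** Simulation with five conditions, n = 50, unit SD, correlation 0.5, Tukey at 0.05 (Aim 2 names no post-hoc method, so Tukey is borrowed from Aim 1), 20,000 trials. The check is passed when hydromorphone exceeds double placebo at two-sided p < 0.05.

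| True state | All three dronabinol contrasts null | Null and check passed |
|---|---|---|
| Measure responds to no drug | 98% | 2% |
| Hydromorphone effect 0.3 SD, no dronabinol effect | 98% | 54% |
| Hydromorphone effect 0.5 SD, no dronabinol effect | 98% | 92% |

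Without the check, the first row cannot be told apart from the other two.

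**4. A floor at $0.** Suppose a share p of participants value the drug. Among them dronabinol adds 0.8 SD of the within-person difference, and hydromorphone exceeds placebo by 0.8 SD. The rest give $0 throughout. The mean difference is 0.8p and its variance is 1.64p − 0.64p².

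- p = 0.3: 0.24 / √0.434 = 0.36 SD
- p = 0.1: 0.08 / √0.158 = 0.20 SD

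I simulated paired t tests with n = 50. The two differences are correlated at −0.5 because both use the hydromorphone + placebo session.

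| Share responding | Null despite a true increase | Same, check passed |
|---|---|---|
| 100% | about 0% | about 0% |
| 30% | about 21% | about 18% |
| 10% | about 82% | about 13% |

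With independent differences the last column becomes about 15% at p = 0.3 and 12% at p = 0.1. The check does most in the extreme case. At 30% the false nulls come mainly from limited power and the absence of a margin, which the check cannot repair.

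**5. Why the check must apply to nulls only.** Suppose every dronabinol comparison were set aside whenever the check failed. With a true dronabinol increase of 0.5 SD and a hydromorphone effect of 0.3 SD, about 44% of trials would have a significant increase relabelled as uninformative. With no hydromorphone effect it would be about 92%.

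**The case against.** **Prior support for sensitivity.** Section 6.a reports data from another ongoing study in which 4 mg gave a mild-moderate effect, neither floor nor ceiling. Section 3 cites hydromorphone effects on QST, and section 6.b reports a moderate analgesic effect after pain testing. This stands for Aim 1 in general. It is not evidence about Drug vs. Money, nor a check on each measure in this sample.

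**Participant screening.** The discrimination exclusion would remove some non-responders. It has no stated criterion, and it relies on a qualifying session that the schedule in section 4.b (one Screening visit and five sessions) does not contain. Those passages must be reconciled. Even if it is applied, it screens people and not the questionnaire.

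**The floor is assumed.** This is correct. No section gives the questionnaire's range or expected values, and section 8.b also refers to people with recreational drug histories.

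**No stated misreading.** A reader might infer that the investigators will report an insensitive measure as proof of safety, or count unresponsive QST measures against enhancement. The documents say neither: they do not say how nulls will be interpreted, and they contain no counting rule. For Aim 1 a null is a failed hypothesis, so insensitivity works against the sponsor.

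**Failing the check is not conclusive.** A reader might also infer that a measure unmoved by hydromorphone says nothing about dronabinol. The background in section 3 proposes synergy, so a measure could respond to the combination, or to dronabinol, without responding to hydromorphone alone.

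**Order.** Hydromorphone + placebo is always Session 1 and double placebo never is. Novelty or habituation could make a measure pass or fail. A session term cannot fully remove this, since Session 1 holds only one condition. This objection stands and limits the check.

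**Conclusion.** The gap is real and matters most for Aim 2, where the predicted result is a null, the test is a difference test, no margin is given, and nothing shows that the outcome can register a drug effect in this sample. A non-significant result could then be taken as support for the hypothesis. For a measure that responds to nothing, about 98% of trials would give that null, against about 2% that would count under the check. With a partial floor the gain runs from small (21% to 18%) to large (82% to 13%). These figures rest on assumed effect sizes, responder shares, correlations and 50 completers. The absence of a rule does not depend on them.

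The point is narrower for Aim 1, where the contrast is already among the Tukey pairs and only a sentence on interpretation is missing. It does not extend to Aim 3, where impairment from dronabinol is itself the question.

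**What to change.** In section 7.a, Primary Aim 2:

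- Name hydromorphone 4 mg + placebo versus double placebo as an assay-sensitivity check on Drug vs. Money.
- If the check is not shown, report a non-significant dronabinol comparison as inconclusive, not as evidence of no increase. Any significant dronabinol increase stands whatever the check shows.
- Report each dronabinol-minus-hydromorphone difference with its confidence interval, so that the size of increase not excluded is visible. Report the share at $0 in each condition.
- State that the check shows sensitivity to hydromorphone only, and that it is confounded with session order because hydromorphone + placebo is always Session 1.

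For Aim 1, add one sentence: where the existing Tukey pair does not separate hydromorphone from double placebo on a QST measure, a null dronabinol result on that measure is reported with that qualification. Do not apply the check to Aim 3.

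The cost is wording plus one contrast on data already being collected. The downside is that some true nulls become inconclusive: the check would fail in about 45% of trials if hydromorphone's effect is 0.3 SD and about 7% if it is 0.5 SD (n = 50, from the power table).

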
refractory pain conditions to widespread societal use for clinical pain.

2. **Objectives** (include all primary and secondary objectives)
 1. **Primary Aim 1: Evaluate the magnitude and duration of combined dronabinol and hydromorphone to reduce pain sensitivity in a validated model of pain.** We hypothesize that the addition of a dronabinol to hydromorphone will result in a dose-dependent increase in the magnitude and duration of analgesia in patients undergoing a validated laboratory model of pain.
 2. **Primary Aim 2: Evaluate the subjective responses to combinations of dronabinol and hydromorphone to determine the subjective, euphoric effects of the combination products.** We hypothesize that dronabinol will not increase the subjective ratings of positive drug effects or other proxy measures of abuse liability, relative to hydromorphone alone.
 3. **Primary Aim 3: Evaluate the degree to which combining dronabinol with hydromorphone impacts neurocognitive performance.** We hypothesize that dronabinol may reduce neurocognitive performance at high doses, relative to hydromorphone alone, though the degree to which this may occur is unknown. This aim is critical for the advancement of potential opioid/cannabinoid combination products.
 4. **Secondary Aim 1: Evaluate whether there are sex differences on study outcomes.** We hypothesize that dronabinol enhancement of hydromorphone-analgesia will be greater among female vs. male subjects.
3. **Background** (briefly describe pre-clinical and clinical data, current experience with procedures, drug or device, and any other relevant information to justify the research).

This study will systematically evaluate whether cannabinoids can enhance the analgesic efficacy of opioids, which will advance the use of cannabinoids for the treatment of acute and/or chronic pain.

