
Conclusion: This will be the 1st human laboratory study to evaluate combinations of cannabinoids and opioids on a comprehensive and validated quantitative sensory testing battery, and the results of this study will identify whether a signal for this medication combination exists that should be advanced into randomized controlled trial evaluations with clinical pain populations. This study will also assess aspects that would impact drug development (abuse liability, neurocognitive impairment) and the effect of participant sex on outcomes. The ultimate goal of this research will be to determine which medication/dose combinations may exert strong analgesic effects, while minimizing abuse liability and cognitive deficits, in order to advance these medications into clinical trials for the treatment of chronic pain. This is a logical first step towards evaluating combined cannabinoid/opioids treatments for chronic pain, and will provide data necessary to support numerous evaluations of combination treatments for this population.

4. Study Procedures

- a. Study design, including the sequence and timing of study procedures (distinguish research procedures from those that are part of routine care).

Project Overview: This study will enroll 100 healthy adults, and will aim to complete 60 (30 men, 30 women) participants. Participants will conduct a within-subject evaluation of the degree to which the FDA-approved cannabinoid dronabinol (Marinol) enhances the analgesic effect of the prototypic opioid hydromorphone (Dilaudid). Subjects will complete a Screening visit to establish study eligibility and 5 experimental sessions. Experimental sessions will occur approximately once weekly and will permit subjects to admit themselves into the clinical research unit the night before the session if interested. Subjects will be provided with taxi service to and from the session. Subjects will receive a dose of hydromorphone (4mg, oral) and a double-blind oral dose of study drug or placebo the

morning of each experimental session, and will undergo QST measures of laboratory evoked pain, provide self-report ratings of drug effects, and complete a neurocognitive battery. The order of sessions will be randomized with the exception of Session 1, which will always be active hydromorphone + placebo to ensure the participant has a safe response to hydromorphone before proceeding into the remaining sessions.

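### The plan does not state that session order is balanced within each sex, so chance order differences can add a small, avoidable error to the sex-by-dose comparison

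*Combined protocol and SAP*

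**What the plan says.** **Order.** Section 4.a (Project Overview): "The order of sessions will be randomized with the exception of Session 1, which will always be active hydromorphone + placebo". The footnote to the dosing table in section 6.a adds: "Sessions 2-5 will be randomized and counter-balanced across participants". The randomized conditions are the three dronabinol doses with hydromorphone, and double placebo. Neither place names sex as a stratum or block, and neither rules it out.

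**Sex.** Section 4.a "will aim to complete 60 (30 men, 30 women) participants". Section 7.c instead plans an "overall completion sample of 50 per study, with subsamples of 25 per group". Under Secondary Aim 1 (section 2): "We hypothesize that dronabinol enhancement of hydromorphone-analgesia will be greater among female vs. male subjects". Section 7.b gives the analysis: "All analyses will be repeated and sex (male/female) will be added as a factor to the analyses".

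**Session effects.** In section 7.a the neurocognitive tests (Aim 3) are compared "using study session number (1-6) as a covariate to control for practice effects". For Aim 1 the text is "Primary outcomes will be tested with repeated two-factor (Drug Condition x Time) models", and Aim 2 uses a repeated measures ANOVA. No session or sequence term is named for Aims 1 and 2.

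**The concern.** Balance over the whole sample cancels a shared drift across Sessions 2-5 from comparisons among the randomized doses. It does not cancel it from the difference between men and women. If one sex happens to receive 10 mg later on average, habituation or sensitization to repeated pain testing enters the male-female difference in the dose effect.

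The sex-by-dose contrast has little precision to spare: its variance is four times that of the corresponding pooled within-participant contrast. The plan already expects a session effect for Aim 3, so allowing for one elsewhere is reasonable. Blocking the order by sex would remove most of this error at the design stage, and it cannot be added once sequences have been allocated.

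**Working it through.** **The plan's own figure.** Section 7.c claims power 0.95 for a main effect of size 0.2 with 6 conditions and 45 participants. Assuming alpha 0.05, correlation 0.5 and sphericity, none of which is stated, a repeated-measures F test gives power 0.962. That figure does not depend on how order is allocated and does not cover the sex-by-dose contrast.

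**Inputs.** n = 30 per sex (section 4.a), or 25 (section 7.c). Randomized positions are Sessions 2 to 5. Hydromorphone alone is at Session 1 in everyone. Drift b is an assumed linear change per session of 0.1, 0.2 or 0.3 within-participant SD, with no session term in the model.

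**Step 1: position variance, V.**
- One dose, uniform over four positions: (4² − 1)/12 = 1.25. This applies to a dose against hydromorphone alone, because the latter's position cannot differ by sex.
- Difference between two randomized conditions, averaged over pairs: 2 × 1.25 × (1 + 1/3) = 3.333.

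**Step 2: SD of the male-female difference in mean position, √(V × 2/n).**
- Dose against hydromorphone alone: √(1.25 × 2/30) = 0.289 sessions (0.316 at n = 25).
- Two randomized conditions: √(3.333 × 2/30) = 0.471 (0.516 at n = 25).

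Simulation of 8,000 allocations per design, balanced overall but not by sex, gives 0.29 for the first at 30 per sex, with mean near zero. For 10 mg against 2.5 mg it gives 0.48 with all 24 orders in use and 0.58 with one four-sequence Williams square. In such a square, two of the six pairs have position differences of ±1 and ±3 (V = 5, SD √(5 × 2/30) = 0.58). The other four have ±1 and ±2 (V = 2.5, SD 0.41).

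**Step 3: variance of the contrast without order error.** In units of the squared within-participant SD this is 2 × (2/n) = 4/30 = 0.133, so the standard error is 0.365. If the dose effect itself varies between people, this is larger and the percentages below shrink.

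**Step 4: added share of variance.** b² × V × (2/n) ÷ (4/n) = b² × V/2. The sample size cancels, so 25 or 30 per sex gives the same percentages.

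| Drift b | Dose vs hydromorphone alone (0.625 b²) | Two randomized conditions, average pair (1.667 b²) | Pair with V = 5 (2.5 b²) |
|---|---|---|---|
| 0.1 | 0.6% | 1.7% | 2.5% |
| 0.2 | 2.5% | 6.7% | 10% |
| 0.3 | 5.6% | 15% | 22.5% |

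**Step 5: power.** For a contrast set at 80% power, the new power is Φ(2.80/√(1 + share) − 1.96). Against hydromorphone alone this gives 79.8%, 79.0% and 77.8%. Between two randomized conditions at b = 0.2 (7% to 10%) it gives about 76% to 77%.

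**Step 6: effect of blocking by sex.** At 30 per sex, the simulated SD for one dose falls from 0.29 to 0.06 (Williams square) or 0.11 (24 orders). For 10 mg against 2.5 mg it falls to 0.12 or 0.19. Added variance against hydromorphone alone is then at most 0.9% at b = 0.3.

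**The case against.** - **Silence is not a decision.** A reader might infer that the sponsor chose not to balance order within sex. The documents do not support that. They name a balancing unit and say no more, and the list may already be blocked by sex. This stands: the point is that balance within sex is not stated.
- **It is noise.** A reader might infer that the sex comparison is biased. Random order keeps the imbalance centred on zero, so the cost is precision only. This stands.
- **The larger percentages are not those of the sex hypothesis.** A reader might attach the 2%, 7% and 15% to Secondary Aim 1. That aim concerns enhancement over hydromorphone alone, whose position is the same in everyone, so the smaller figures apply. The larger ones matter for sex differences between doses or against double placebo, which are 6 of the 10 pairs among five conditions. This stands.
- **Baselines absorb drift.** Section 4.a takes a pre-dose baseline in every session, and change scores would subtract some drift. Section 7.a makes the transformation conditional on large baseline variation for the raw pain data, although some measures are specified relative to baseline. No pre-dose baseline is described for the Drug vs. Money questionnaire. This stands in part.
- **A session covariate would suffice.** It would remove linear drift common to both sexes, which is most of the issue. It would not remove drift that is non-linear or differs by sex. Balance within sex covers those cases for contrasts between randomized conditions. It cannot remove sex-specific drift from comparisons with hydromorphone alone, because that condition always comes first.
- **Dropout.** Section 4.a enrols 100 to complete 60, so exact balance among completers cannot be promised. This stands, but blocking still gives a better starting point.

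**Conclusion.** The point holds as a minor, inexpensive design improvement. The plan states counter-balancing across participants but not within each sex, plans a sex-by-dose comparison, and names no session term for Aims 1 and 2. For the stated sex hypothesis the cost is well under one point of power at drift 0.1, about one point at 0.2 and about two points at 0.3. It is larger for sex differences between randomized conditions: about 2%, 7% or 15% added variance on average, and more for some pairs.

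These sizes rest on an assumed linear drift that the documents do not give, on no session adjustment, and on no removal of drift by baseline correction. They do not show that any trial conclusion would change.

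**What to change.** Amend the dosing-table footnote in section 6.a and the pharmacy list so that the Sessions 2-5 order is generated separately for men and for women, in blocks of four sequences that form one balanced 4 × 4 Williams square. Sequence counts among those allocated within each sex are then nearly equal (for 30, seven full blocks plus two). Dropout may loosen this among completers. If the list is already built this way, the footnote need only say so.

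As a complement, add session number to the Aim 1 and Aim 2 models in section 7.a, as for Aim 3. Use a numeric covariate: as a categorical factor, Session 1 would coincide exactly with hydromorphone alone. The two changes belong together, because without the session term the drift stays in the residual and the reported standard error does not show the full gain from blocking. The session range given for Aim 3 (1-6) should be reconciled with the five sessions planned.

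The cost is two lists in place of one and a few words in the analysis section. No dose, visit, assessment or participant number changes, and sex is already a recruitment quota.
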